Appendix 5 – Flow diagram for subject recruitment, selection, and study design

Appendix 6 – Checklist for study procedures to be performed

Schedule of Activities

Session	1	2
Obtain informed consent.	X	
Confirm eligibility/enroll.	X	X
Medical history and vital signs.	X	X
Sialometry test	X	X
Test 1 (Biotene or Water)	X	
Post-test Survey of First Product	X	

[figure not shown]
Medical history and vital signs.		X
Test 2 (Biotene or Water)		X
Post-test Survey of Second Product		X
Post-test survey of xerostomia experience.		X

Appendix 7 - Patient Xerostomia Experience and Severity Questionnaire
Continuous variables recorded on a visual analogue scales (VAS)

[figure not shown]
Chart number: _____ Subject's Initials: _____ Date: ___/___/___

Please respond to the following questions by *placing a single mark on the line*.
 The numbers below the scale are references only.

[figure not shown]
Acceptable:

[figure not shown]
Not acceptable:

[figure not shown]
1. How dry is your mouth? (Extremes: 0 = 'not dry at all', 10 = 'worst imaginable dryness')

[figure not shown]
2. Do you have difficulty chewing because of your dry mouth? (Extremes: 0 = 'no difficulties at all', 10 = 'very severe difficulties chewing')

[figure not shown]
3. Do you have difficulty swallowing because of your dry mouth? (Extremes: 0 = 'no difficulties at all', 10 = 'very severe difficulties swallowing')

[figure not shown]
4. Is speech difficult because of your dry mouth? (Extremes: 0 = 'no difficulties at all', 10 = 'very severe difficulties with speech')

5. Is taste affected by your dry mouth? (Extremes: 0 = 'not affected at all', 10 = 'very severe alteration of taste')

6. Do you have a burning sensation in your mouth? (Extremes: 0 = 'no burning at all', 10 = 'very severe burning mouth')

**Appendix 8 – Sample data collection form for unstimulated whole saliva flow rates
(mL/min)**

[figure not shown]
Subject ID	Date	Subject Age	A -Wt of collected saliva (mg)	UWSFR 1 (A / 15 min)*	Date	B -Wt of collected saliva (mg)	UWSFR 2 (B/ 15 min)*
174							
938							
235							

* Calculation based on specific gravity 1 mg = 1 mL

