5. METHODS AND STUDY PROCEDURES

5.1.1. Treatment Dosage and Administration.

The methods and study procedures will consist of the following 11 parts which will be completed during a recruitment encounter and two testing visits. (See also Appendices 5 and 6).

Recruitment Encounter

This will be brief and will occur at the time the potential subject volunteers to be considered for the study. (Please see below for details.)

Visit 1

1. Sign consent form (if not completed at Recruitment Encounter.)
2. Update of medical history and recording of blood pressure and pulse.
3. Questionnaire about subject's xerostomia experience.
4. Determination of unstimulated whole saliva flow rate.

The inclusion criteria for the study require that the rate be ≤ 0.2 mL/min. A subject's participation will be terminated at this point if this inclusion criterion is not met.

5. Trial with randomly assigned alternative or experimental agent.
6. Post-test study questionnaire about study agent.

Session 1 is complete at this point. An appointment will now be scheduled for Session 2.

Washout Period

As is usual in studies utilizing a crossover design a "washout period" will be employed in this investigation. The retention time appears to be related to the viscosity of a topical agent for the relief of a dry mouth (Shahdad et al. 2005). Therefore, a washout period of at least 48 hours, to be utilized here, appears to be sufficient to eliminate the effects of a single application of Biotène.

Visit 2

1. Update of medical history and recording of blood pressure and pulse.
2. Determination of unstimulated whole saliva flow rate. Subjects will continue in the study regardless of their salivary flow rate at this point. The mean of the UWSFRs measured at Sessions 1 and 2 will be used in calculations comparing flow rates to duration of action of the two agents. This will be done as a matter of interest in the amount of variation that may exist between the 2 UWSFR measurements.
3. Trial with either control or experimental agent, whichever was not tested in Session 1.
4. Post-study questionnaire about study agent, whichever was not tested in Session 1.

Each of the two testing visits is expected to utilize as much as three (3) hours but may be less, depending mainly on subjects' responses to the test agents. Both sessions will be

scheduled in the time period 830am – 1230pm to control for known variations in daily flow rates.

Detailed descriptions of each part follow here.

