Recruitment Encounter

This encounter would commonly occur during or after a routine clinic visit or otherwise after s/he learns of the study. At this time the investigator would read to the potential subject a scripted question plus a limited statement of eligibility. If the investigator continues to feel that the subject may be eligible s/he will be encouraged to sign the consent form. At the potential subject's request s/he may take the consent form for the purpose of further consideration personally or with family, other health professionals, etc. and return it at the first experimental visit. (See Appendix 1 for Scripted Recruitment Statement).

Visit 1

1. Sign consent form if this was not done at the Recruitment Encounter. Update of subject's medical history and measurement of vital signs (blood pressure, pulse, respiration rate, presence and level of any pain.).

2. As also indicated previously, when subjects are initially contacted about the study they will be given a consent form to take with them and consider participation, possibly including discussions with family, health professionals, etc., and then return to the investigator. If any questions exist the investigator will respond and then require that the consent be signed by both the investigator and subject prior to proceeding. A copy of the signed form will be given to the subject and the original retained by the investigator in a locked file in a University facility accessible only to investigators.

3. Survey of Experience with Xerostomia. (Appendix 7)
 A secondary aim of the study is to gather qualitative information about subjects' experiences with xerostomia. A tested 6-item written questionnaire will be administered at this time.(Shahdad et al, 2005) for this purpose. The time needed for completion of this brief questionnaire is estimated at 5 minutes.

4. Determination of Unstimulated Whole Saliva Flow Rate. (UWSFR) (See Appendix 8)
 The purpose of this test is to determine whether or not potential subjects have a rate of not more than 0.2 mL/min. The UWSFR test will be completed in a quiet room with lighting generally at a low level but bright enough to allow for reading. Subjects will be seated in a cushioned chair and encouraged to make themselves as relaxed and comfortable as possible. A pre-weighed plastic disposable drinking cup (+/- 0.01 g) will be given to the subject with instructions to cease the normal process of swallowing when

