saliva accumulates but rather allow it to accumulate in the mouth and then drain gently into the cup. The time will be noted by the investigator and, after 15 minutes, the investigator will advise the subject that the test has ended. The investigator will again weigh the cup and saliva and record the weight. One gram will be understood to be approximately equivalent to 1 mL of saliva and the new weight recorded. The weight per minute will be calculated and understood to be the subject's current unstimulated whole saliva flow rate (UWSFR). If the rate is < 0.2 mL/min the subject will be advised that the inclusion criteria for the remainder of the study have been met and that the study will continue. This level was selected as a "cut-off" both because it is the level at which existing literature recognizes genuine mouth dryness to likely exist and also because of our belief that subjects who perceive dryness in the presence of relatively 'normal' salivary flow rates, may be unreliable in their reports of beneficial effects of study agents. Subjects who do not meet the inclusion criteria will be given \$25 in appreciation for their participation to this time and then dismissed.

6. First Test agent.

The subject will then be seated in a quiet dimly lit room and asked to refrain from speaking, including using phones, unless it is essential (e.g. they are feeling badly enough that their participation needs to be paused or stopped). After not less than one (1) minute a visual analog scale (VAS) of dryness will be recorded in response to the question, "How much discomfort are you feeling from your dry mouth?". (See Appendix 9). They will then be administered, by the investigator, a dose of 3 sprays (to the anterior dorsal of the tongue) of the randomly selected experimental or alternative agent with instructions to "spread it around in your mouth." An electronic timer will be started by the investigator at that time. The investigator will be administering the agents after priming the spray bottle twice before aiming the first spray to the anterior dorsal of the subject's tongue. Neither the investigator nor the subject will know the identity of the administered agent.

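### The Appendix 8 flow-rate form works in mg with 1 mg = 1 mL, which contradicts the 1 g = 1 mL procedure in Section 5.1.1 by a factor of 1000; the headings and footnote need a unit correction

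*Combined protocol and SAP*

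**What the plan says.** **Procedure (Section 5.1.1, Visit 1, UWSFR test).** The precision of the weighing is given in grams: "A pre-weighed plastic disposable drinking cup (+/- 0.01 g) will be given to the subject". After 15 minutes, "The investigator will again weigh the cup and saliva and record the weight". The conversion is then stated: "One gram will be understood to be approximately equivalent to 1 mL of saliva". The weight per minute is taken as the flow rate. The heading of this step sends the reader to the form: "Determination of Unstimulated Whole Saliva Flow Rate. (UWSFR) (See Appendix 8").

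**Form (Appendix 8).** The title gives the rate in mL/min. Column A (first measurement) and column B (second measurement) are both headed "Wt of collected saliva (mg"). The rates are A / 15 min and B / 15 min, with no factor of 1000. The footnote reads "Calculation based on specific gravity 1 mg = 1 mL".

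**Use of the result.** The inclusion criterion in Section 3.2 is a rate of 0.2 mL/min or less. At Visit 1 a subject's "participation will be terminated at this point if this inclusion criterion is not met". At Visit 2 the rate no longer decides anything: "Subjects will continue in the study regardless of their salivary flow rate at this point". Section 5.1.1 then uses the mean of the two rates when flow is compared with duration of action.

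**The concern.** The procedure and its form give different conversions for the same measurement. This is unlikely to be an artefact of reading the PDF, because mg appears in both column headings and in the footnote, and all three agree. The likely cause is mg written where g was meant.

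The form deserves attention because it is the only flow-rate form in the document and the procedure cites it. At stake in principle are the Visit 1 eligibility decision, the mean UWSFR, and the sialometry result that goes into the dental chart (Section 12) and is offered to subjects (Section 5.9). The practical hazard is mixed units: one entry made in mg as the heading asks, another in g as the balance reads, with nothing on the form to tell them apart.

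**Working it through.** **Inputs**
- Collection time: 15 min (Section 5.1.1 and Appendix 8).
- Eligibility limit: 0.2 mL/min (Section 3.2).
- Procedure conversion: 1 g ≈ 1 mL (Section 5.1.1).
- Form conversion: 1 mg = 1 mL, rate = A/15 with A in mg (Appendix 8).
- Weighing precision: ±0.01 g = 10 mg (Section 5.1.1).

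**Step 1. Weight at the limit under the procedure.** 0.2 mL/min × 15 min = 3.00 mL, so 3.00 g or 3000 mg. Check: 3.00/15 = 0.2 mL/min.

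**Step 2. The same samples under each way of using the form.**

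| Saliva in 15 min | Procedure, g/15 (mL/min) | Form followed literally, mg/15 (mL/min) | Grams entered under the mg heading, A/15 (mL/min) |
|---|---|---|---|
| 0.75 g = 750 mg | 0.05 | 50 | 0.05 |
| 1.50 g = 1500 mg | 0.10 | 100 | 0.10 |
| 3.00 g = 3000 mg | 0.20 | 200 | 0.20 |

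The literal result is 1000 times the procedure's in every row (200/0.2 = 1000). Entering grams gives the correct rate.

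**Step 3. The printed rule read backwards.** A rate of 0.2 mL/min at 1 mg = 1 mL corresponds to 0.2 × 15 = 3 mg = 0.003 g, which is 0.003/0.01 = 0.3 of the stated precision. This restates the same factor of 1000. It shows that the printed rule and the stated balance cannot both be intended.

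**Step 4. Would a partial correction do?** No. If only the footnote is changed to 1 g = 1 mL while the columns stay in mg, A/15 still gives 3000/15 = 200. If only the headings are changed to g, the arithmetic comes right but the footnote still contradicts it. With both changed, 3.00/15 = 0.2. If mg is kept, 3000/(1000 × 15) = 0.2.

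**Step 5. Effect on the comparison of flow with duration.** If every rate were 1000 times too large, a correlation with duration would not change. Mixed units would distort it. As a hypothetical, a subject with a true rate of 0.2 mL/min at both visits, calculated from g at one and from unconverted mg at the other, would have a mean of (0.2 + 200)/2 = 100.1 mL/min.

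**The case against.** The strongest case for leaving this alone is that it is one unit slip on a form labelled as a sample. The procedure is complete and correct without it: it weighs in grams, gives the right conversion, divides by time, and the limit is stated in mL/min. A balance that reads in grams invites entry in grams, and that gives the right answer. Literal use would mostly expose itself, since rates of 50 to 200 mL/min are far outside anything the plan expects. A uniform error would not alter a correlation, and the duration outcome is recorded on a separate form (Appendix 10).

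All of this stands and limits the size of the point. It does not remove it. The rate comes right only if the user disregards both headings and the footnote of the form that the procedure cites.

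A reader might infer more than the documents support:
- **That subjects were wrongly screened out, or that nobody could qualify.** This would need staff to convert gram readings to mg, apply the footnote, ignore Section 5.1.1 and accept implausible rates. Nothing shows that this happened.
- **That existing data are in the wrong unit.** Appendix 13 refers to data already collected, so completed forms may exist. That script concerns age eligibility and says nothing about which form or unit was used.
- **That the flow-duration comparison is compromised.** Only mixed units would do that, and the documents give no sign of mixing.

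**Conclusion.** The contradiction is certain and its factor is exactly 1000: 200 instead of 0.2 mL/min at the eligibility limit if mg are entered and the form is followed as printed. It is a minor but definite error on the form used for the eligibility measurement and the mean UWSFR, and it should be corrected. No misclassification, wrong result or effect on the duration outcome is shown, and the pilot sample size of 20 is not affected.

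The factor rests only on figures printed in Section 5.1.1 and Appendix 8. That mg was a slip for g is an inference, though the gram precision of the weighing supports it. Which unit was used in practice cannot be known from the documents.

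**What to change.** Correct Appendix 8 in one of two ways, changing all the linked items together:
- **Grams:** head columns A and B in g and change the footnote to 1 g = 1 mL. A/15 and B/15 then stand.
- **Milligrams:** keep the headings, print A/(1000 × 15) and B/(1000 × 15), and change the footnote to 1000 mg = 1 mL.

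The first matches the procedure and the stated weighing precision. Either way, the footnote should not call the conversion a specific gravity, which has no units; mass per volume is a density.

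If completed forms exist, confirm against the recorded cup weights that one unit was used throughout.

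The cost is two headings and one footnote, or two formulas and one footnote, plus a short source check if forms have been filled in. No new measurements are needed.

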Appendix 9 - Level of discomfort a patient is feeling on a visual analog scale.

Chart number: _____ **Subject's Initials:** _____ **Date:** ___/___/___

How much discomfort are you feeling from your dry mouth? (Extremes: 0 = 'no discomfort', 100 = 'worst imaginable discomfort/dryness')

Appendix 10 – Sample data collection form for endpoint and VAS scores.

Subject ID	VAS scores on a 100 mm scale (t = time elapsed in minutes)										End-point (min) ¹	VAS score at Endpoint (mm)
	$t=0^*$	$t=1$	$t=15$	$t=30$	$t=45$	$t=60$	$t=75$	$t=90$	$t=105$	$t=120$		
174												
938												
235												
379												

¹The endpoint of the retention time is defined as when the subject has perceived that the effect of the agent has dissipated, or after 2 hours has elapsed. The retention time will therefore be from the time the agent is administered to the endpoint.

* Timepoint before the test agent is administered

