One minute after the spray a second VAS will be recorded. For every 15 minutes elapsed, the investigator will repeat the question, "How much discomfort are you feeling from your dry mouth?" Subjects' responses will be recorded each time. Subjects will be instructed to stop the timer when they feel that the effect of the administered agent has dissipated completely (Appendix 10).

Studies with other more viscous moisturizing agents have rarely found the duration of effect to be more than two (2) hours. Therefore, the maximum amount of time subjects in this study will be tested is two (2) hours (Jose et al, 2016). The endpoint for each subject, however, will occur the subject feels that the effect of the agent has dissipated; the

duration of effect will be the time between starting the timer and the elapsed time to the endpoint.

6. Survey of Experience with First Test Agent.

A secondary objective of this study is to gather new information about subjects' perceptions of the characteristics of agents designed to relieve xerostomia. However, a review of literature utilizing PubMed and references from other investigations did not reveal a standardized survey tool for this objective. Therefore a new post-test questionnaire about agents designed to ameliorate xerostomia was designed by investigators and will be administered (Appendix 11). This information could be useful in the subsequent full study to help determine whether or not further efforts are needed to mask any potentially noticeable differences between agents being tested. This is a 9-item survey of a variety of characteristics of potential agents. A printed copy of the survey attached to a clipboard and also a black-ink pen will be handed to the subject. The subject will be instructed to circle the best answers and then return. The use here of this questionnaire will constitute a pilot study because it is new and has not yet been validated.

At this time the subject will be given a check for \$25, an appointment for the second visit, and dismissed for the day.

Washout Period

A period of at least 48 hours will be required prior to Visit 2.

Visit 2

1. Update of medical history and recording of blood pressure and pulse.
2. Second sialometry to determine a second UWSFR.

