3. Administration of second test agent (which ever was not used in Session 1). Recordings of VAS regarding the feeling of dryness will be made just before and after administration of the test agent and then every 15 minutes in a manner identical to that of Session 1. Subjects will be instructed to stop the timer when they feel the effect of the test agent has dissipated completely; this will mark the endpoint of the duration of effect, which will be recorded.
4. Survey of experience with second test agent.

This will utilize the same survey form used in Session 1 (Appendix 11).

At this point, the subject has completed the required commitment to the study, and will be de-briefed, including being requested to verbally supply any comments they feel might be useful in future studies in which they might participate. Subjects will be offered additional

information and/or referrals to a dry mouth clinic as needed. They will be compensated \$50 plus parking for their participation and dismissed.

(See also Appendices 4 and 5 for flow chart and schedule of activities.)

5.1.2. Amount of agent to be tested. And 5.1.3. Investigational drug/device.

The manufacturer of Biotène Moisturizing Mouth Spray has directions (Appendix 12) printed on the spray bottle stating, “Spray directly into the mouth, onto the tongue, and spread thoroughly inside the mouth. Use as required. Safe to swallow when used as directed.” In an effort to minimize variation in the amount dispensed for this study but to remain essentially consistent with the manufacturer’s directions the investigator will assume the following calibration protocol for each subject:

1. Weigh the empty cup to be used for collection of whole saliva.
2. Prime the spray bottle by squeezing firmly at least twice, toward a sink or bucket. This “spray sample” will then be discarded.
3. Using the identical technique, three sprays will then be collected in a second empty cup and weighed. This will serve as a “calibration sample.” This sample will then be discarded but the empty cup retained.
4. The investigator will then direct three sprays to the anterior dorsal of the tongue. Utilizing a total of three sprays is intended to mimic what a xerostomic patient likely would do. Having the investigator, instead of the subject, administer the agent is expected to make the amount of agent expressed be generally uniform among subjects.

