5.2. Efficacy Assessment

This pilot study was developed because estimated data regarding the duration of action of a single dose of Biotène Moisturizing Mouth Spray is not available. The estimated duration is necessary for calculating the sample size for a definitive study. At the completion of the pilot, the mean duration of action of both the experimental and control agents will be forwarded to the biostatistician ([name]) for calculation of the sample size for the definitive study. When the required sample size is returned to investigators, plans for the definitive efficacy assessment will be developed.

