Appendix 11 - Subject evaluation of test agent

Chart number: _____ Subject's Initials: _____ Date: ___/___/___

1. How quickly did the product provide relief of your dry mouth symptoms?

- Immediately
- In minutes
- Did not provide relief

Please rate your responses to the following statements by circling the best answer:

2. The taste of the product was tolerable

Strongly disagree Disagree Not sure Agree Strongly agree

3. The thickness of the product was acceptable

Strongly disagree Disagree Not sure Agree Strongly agree

4. I would like to continue using this product

Strongly disagree Disagree Not sure Agree Strongly agree

5. I would purchase this product to use on a regular basis

Strongly disagree Disagree Not sure Agree Strongly agree

6. This product is easy to use

Strongly disagree Disagree Not sure Agree Strongly agree

7. I would prefer using another product

Strongly disagree Disagree Not sure Agree Strongly agree

8. At today's visit, you sampled either a commercially available moisturizing spray or a standard therapy recommended by physicians. Which product do you think you received today?

- Moisturizing spray
- Standard therapy
- Not sure

9. Can you name a preferred product ? _____

10. How long ago did you have anything to eat or drink today? Please choose the best response.

- Less than 1 hour ago
- Approximately 1 hour ago
- Approximately 2 hours ago
- Approximately 3 hours ago
- I did not eat or drink anything this morning

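### The endpoint rule has no branch for a subject who feels no effect, so non-response can be recorded anywhere from about 0 to 120 min, including at the same value as full 2-hour relief

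*Combined protocol and SAP*

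**What the plan says.** Section 5.1.1 defines the endpoint by perception: "The endpoint for each subject, however, will occur the subject feels that the effect of the agent has dissipated". The Visit 1 instruction is "Subjects will be instructed to stop the timer when they feel that the effect of the administered agent has dissipated completely", and Visit 2 repeats it for the other agent: "Subjects will be instructed to stop the timer when they feel the effect of the test agent has dissipated completely". Observation is limited: "Therefore, the maximum amount of time subjects in this study will be tested is two (2) hours". The Appendix 10 footnote joins the two conditions, so the endpoint is "defined as when the subject has perceived that the effect of the agent has dissipated, or after 2 hours has elapsed", and then fixes the recorded value: "The retention time will therefore be from the time the agent is administered to the endpoint".

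The protocol foresees subjects who get nothing from an agent. Item 1 of the Appendix 11 survey, completed after each agent, offers the answer "Did not provide relief". Nothing connects that answer to the duration entered on the Appendix 10 form. The form itself has no zero code and no field for absence of effect.

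Section 5.2 states what the durations are for: "the mean duration of action of both the experimental and control agents will be forwarded to the biostatistician", so that the definitive study can be sized. Sections 13.1 and 13.2 give no rule for non-responders or for values at the 2-hour limit.

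**The concern.** The rule offers two exits: the effect is felt to have gone, or 2 hours pass. A subject who felt nothing has no effect to perceive going. Following the instruction to the letter, that subject leaves the timer running and exits at 2 hours. The form then shows 120 min, the best possible result, for the worst possible outcome. A second subject with the same experience may reason that the effect is already absent and stop the timer at once. The documents support either action, so one clinical state has no defined duration.

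Duration is the study's main outcome, and its mean by agent is what the pilot passes on for planning. Values misplaced at 120 raise that mean. They also widen the spread when responders' durations are mostly short. If they fall unequally on the two agents, they change the contrast on which the definitive study is sized.

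**Working it through.** **The plan's own figure.** The only sample size given is 20 for the pilot (Sections 3.1 and 13.1), on the biostatistician's recommendation. No alpha, power, SD or difference is stated, so it cannot be reproduced. The point does not depend on how 20 was reached.

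**Tracing the rule for a subject who feels no effect**
- Literal reading: no dissipation is perceived, the timer is not stopped, the 2-hour condition applies, and the entry is 120 min.
- Looser reading: the subject treats absence of effect as complete dissipation and stops the timer near 0.
- A subject with full 2-hour relief is also entered at 120 min. The duration field cannot separate this from the first case.

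**Shift in an agent's mean.** With k non-responders among 20 subjects entered at 120 instead of 0, the shift is k × 120/20 = 6k min: 6 min for one, 12 for two, 24 for four. This needs only the pilot size and the 2-hour limit.

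**Illustration of the effect on sizing.** None of these inputs is in the documents. Assume responder durations are exponential with mean 60 min (spray) and 25 min (water), capped at 120, and independent between agents; non-response is 5% on spray and 20% on water; two-sided alpha is 0.05 and power 90%. Let f be the fraction of non-responders entered at 120, with the rest at 0.

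- Capped responder mean, m(1 − e^(−120/m)): 60 × (1 − 0.1353) = 51.88; 25 × (1 − 0.0082) = 24.79.
- Capped second moment, 2m² − 2m·e^(−120/m)·(120 + m): 4276.8 and 1190.3.
- Agent mean = (1 − p) × capped mean + p·f·120. Variance = (1 − p) × second moment + p·f·14,400 − mean².
- SD of the difference = square root of the sum of the two variances.
- Paired n = (1.96 + 1.2816)² × SD²/difference² = 10.51 × SD²/difference².

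| Fraction of non-responders at 120 | Spray mean | Water mean | Difference | SD of difference | Paired n |
|---|---|---|---|---|---|
| None | 49.3 | 19.8 | 29.5 | 46.8 | about 27 |
| A quarter | 50.8 | 25.8 | 25.0 | 51.7 | about 45 |
| Half | 52.3 | 31.8 | 20.5 | 55.4 | about 77 |
| All | 55.3 | 43.8 | 11.5 | 60.3 | about 290 |

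**Equal non-response.** With 5% on both agents, the difference is 25.7 min whether non-responders are entered at 0 or 120. The SD rises from 47.0 to 52.0 and n from about 35 to about 43.

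**When the sign would reverse.** With 5% non-response on spray and every non-responder at 120, the spray mean is 55.29. The water mean is 24.79 + 95.21p, which exceeds 55.29 when p is above 30.50/95.21 = 0.32.

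**A second set of assumed inputs.** Take responders' mean (SD) as 45 (25) min on spray and 20 (15) on water, 80% power, correlation 0 to 0.5, and non-response of 10% versus 20%. Paired n is 8 to 13 if non-responders are entered at 0 and 74 to 144 if all are entered at 120. With 10% versus 40%, all at 120, the means are 52.5 (spray) and 60.0 (water), so the sign reverses.

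**The case against.** **The plan is silent and does not assign 120.** A reader might infer that every non-responder is entered at the maximum. The documents do not support that: a subject asked to stop once the effect is completely gone may well stop near 0. This objection stands. What remains is that the literal reading leads to 120 and no text rules it out.

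**Effect is not the same as relief.** The timer instruction concerns the agent's effect; Appendix 11 item 1 concerns relief of symptoms. A subject might feel wetness fade, stop the timer, and still report no relief. This also stands. A no-relief answer alone does not show that a 120 is wrong, so item 1 can serve as a check but not as the definition.

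**More non-response on water is not documented.** It is plausible, but neither agent's no-relief rate is given. Section 5.1 quotes 49.5% favourable ratings at 2 hours from a published study, for the spray only. The direction of any bias therefore rests on an assumption.

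**The data to spot the problem are collected.** VAS is taken before the spray, at 1 minute, every 15 minutes and at the endpoint, under supervision. A 120 with a flat VAS and a no-relief answer could be noticed. But nothing in the plan uses these data to set or correct a duration, so any correction would be an unplanned decision about the main outcome.

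**It is only a pilot.** True, and no confirmatory test is specified. But supplying these means is the pilot's purpose, so an error in them carries into the definitive study.

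**Conclusion.** The concern holds as a gap in the endpoint definition. A subject who feels no effect has no defined duration, the literal reading gives 120 min, and the same state can be entered anywhere from about 0 to 120. The firm size is 6 min on an agent's mean for each such subject entered at 120 instead of 0, among 20.

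Two stronger conclusions are tempting and unsupported. The first is that the control mean will be inflated and the contrast shrunk or reversed; that needs more non-response on water, which no section states. The second is that the planned sample size would rise about tenfold, from 27 to 290; that needs 5% versus 20% non-response and every non-responder running to 2 hours. Under the same assumed durations, n is 45 if a quarter do, 77 if half do, and 43 against 35 when non-response is 5% on both agents. The sample sizes show only how sensitive planning is to the missing rule.

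**What to change.** In Section 5.1.1 (both visits) and the Appendix 10 footnote:

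- Define duration as 0 when the subject reports that no effect was felt at any time, whatever the timer shows.
- Add a tick box to Appendix 10 for no effect felt at any time. Complete it at the end of the observation and check it against the VAS series and Appendix 11 item 1. Do not decide it at the 1-minute VAS: item 1 allows for relief that arrives within minutes, and an early decision could misclassify delayed responders.
- Reserve 120 for subjects who still feel an effect at 2 hours, and flag those values as censored.
- With the mean durations sent to the biostatistician, report by agent the number with no effect and the number censored.

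Appendix 13 shows that some subjects had already taken part. For their records only the VAS and item 1 are available, so the handling rule should be written down before the bottle codes are opened.

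Cost: one tick box and one line of reporting. No extra visits or subjects are needed.
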